### **9.2.4 Pregnancy Testing**

A urine or serum pregnancy test will be obtained from female subjects who are of childbearing age prior to their participation in the study. These measurements will be performed as outlined in the Schedule of Events.

### **9.2.5 Hepatitis B Testing**

Participants will undergo Hep B surface antigen testing at Screening, if they have not had such screening within the preceding 6 months. Individuals with active Hep B will be excluded. This is defined as detectable Hep B surface antigen. Individuals without detectable Hep B surface antigen will remain eligible, regardless of their vaccination or antibody status (e.g., a positive Hep B cAb or negative Hep B sAb is not exclusionary).

### **9.2.6 Hepatitis C Testing**

Participants will undergo Hep C antibody testing at Screening, if they have not had such screening within the preceding 6 months. Individuals with active Hep C, defined as positive or indeterminate antibody with the presence of Hep C RNA, will be excluded. Positive or indeterminate Hep C Ab in the absence of Hep C RNA is not exclusionary.

### **9.2.7 HIV Testing**

HIV antibody testing will not be required prior to participation in the study but can be performed at the discretion of the PI if requested by a study volunteer. A history of HIV infection on its own is not exclusionary. Participants with controlled HIV infection will remain eligible for the study. If a potential participant is HIV positive, up to 6 months of medical records preceding the Screening visit will be reviewed to evaluate for virus control. Individuals with HIV who are viremic and not on ART will be excluded. Furthermore, those with 2 or more consecutive, quantifiable plasma HIV RNA levels >48 copies/mL in the preceding 6 months, even if on ART, will be excluded. Finally, a plasma HIV RNA test will be performed as part of the Screening procedures for any participant known or found to be HIV positive, if such a test is not available in the 60 days preceding the Screening date.

### **9.2.8 SARS-CoV-2 PCR or Antigen Testing**

Swabs of the anterior nares and/or nasopharynx will be performed to assess for SARS-CoV-2 shedding as outlined in the Schedule of Events.

## **9.3 Research Laboratory Measurements**

### **9.3.1 Plasma Measures of Viral Persistence**

Plasma levels of SARS-CoV-2 antigens (Spike, nucleocapsid, etc.) may be performed in collaboration with research laboratories to evaluate the effect of mAb therapy on measures of viral persistence.

### **9.3.2 Immunophenotyping**

Single- or multi-plex platforms will be used to measure targeted biomarkers previously shown to be elevated in Long COVID, which may include interleukin-6, tumor necrosis factor-alpha, monocyte chemoattractant protein-1, and interferon-gamma induced protein 10. In addition, we will use high-throughput platforms such as Olink proteomics to conduct within-person and/or between-group comparisons in order to identify pathways that are altered with treatment, or that differ between those with and without improvement during the study period. Additional measures of cellular and humoral immunity may also be performed.

### **9.3.3 Pharmacokinetic (PK) analyses**

Blood samples for determination of serum concentrations of AER002 will be collected at following timepoints:

- Pre-dose
- Post dose:
  - 1 hour (acceptable +/- 10 min)
  - D15 (acceptable +/- 3 Days)
  - D30 (acceptable +/- 5 Days)
  - D90 (acceptable +/- 14 Days)
  - D180 (acceptable +/- 14 Days)
  - D360 (acceptable +/- 28 Days)

### **9.3.4 Immunogenicity analyses (ADA)**

Blood samples for determination of Anti-drug antibodies (ADA)s of AER002 will be collected at following timepoints:

- Pre-dose
- Post dose:
  - 1 hour (acceptable +/- 10 min)
  - D15 (acceptable +/- 3 Days)
  - D30 (acceptable +/- 5 Days)
  - D90 (acceptable +/- 14 Days)
  - D180 (acceptable +/- 14 Days)
  - D360 (acceptable +/- 28 Days)

If no ADA are detected through Day 90, the D180 and D360 analyses will not be performed.

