### 8.2 Blinding

Treatment assignments will be blinded to the investigator, subjects, and all clinical and research staff for the entire study, except for designated pharmacy staff or delegate who will remain unblinded to prepare the study drug or placebo.

Unblinding can occur at any time for a medical emergency or any other significant medical event and when a treatment decision is contingent on knowing the subject's treatment assignment. When possible, the investigator or delegate should discuss with Aerium Therapeutics prior to unblinding. The date and reason for unblinding must be recorded and Aerium Therapeutics will be notified.

The Safety Monitoring Committee (SMC) may review any unblinded clinical analysis during the study and provide the recommendations to the Investigator. Subject level unblinded data will not be shared with the Investigator until the end of the trial.

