## **9 STUDY PROCEDURES AND GUIDELINES**

A Schedule of Events representing the required testing procedures to be performed for the duration of the study is diagrammed in Appendix 1. The Schedule of Events will serve as the final resource for guiding study activities.

Prior to conducting any study-related activities, written informed consent and the Health Insurance Portability and Accountability Act (HIPAA) authorization must be signed and dated by the subject or subject's legal representative. If appropriate, assent must also be obtained prior to conducting any study-related activities.

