## APPENDIX 1. SCHEDULE OF EVENTS

Target Day	-28	-7	0	1	15	30	90	180	360
Visit Name	Screen	Baseline	Intervention	Phone FU	2W	1M	3M	6M	12M
Visit Window	-28 to -8	-21 to -1	N/A	+1	+/-3	+/-5	+/-14	+/-14	+/-28
Screening Procedures									
Informed Consent	x								
Eligibility Review	x								
Screening Labs	x								
Demographics	x								
Medical History (inc. ME/CFS, hEDS, EM, MCAS assess.)	x								
COVID-19 History	x								
Concomitant Medications	x	x	x	x	x	x	x	x	x
Study Product Administration									
Randomization			x						
AER002 vs Placebo			x						
Clinical Assessments									
Vital Signs	x	x	x 		x	x	x	x	x
Physical Assessment	x	PRN	PRN		PRN	PRN	PRN	PRN	PRN
Long COVID Symptom Assessment (LIINC Quest.)	x	x	x		x	x	x	x	x
Quality of Life, (e.g., EuroQoL)	x	x			x	x	x	x	x
PROMIS-29	x	x			x	x	x	x	x
PGIC Scale						x	x	x	x
Duke Activity Status Index	x	x			x	x	x	x	x
Post-COVID Functional Scale	x	x			x	x	x	x	x
Dysautonomia Assessment (e.g., COMPASS-31)		x					x	x	x

Target Day	-28	-7	0	1	15	30	90	180	360
Visit Name	Screen	Baseline	Intervention	Phone FU	2W	1M	3M	6M	12M
Visit Window	-28 to -8	-21 to -1	N/A	+1	+/-3	+/-5	+/-14	+/-14	+/-28
DSQ-PEM		x		x	x	x	x	x	x
WHO-DAS		x					x	x	x
Neurocognitive assessment (e.g., NIH Toolbox)		x					x	x	x
6MWT		x			x	x	x	x	x
Safety Outcomes									
AE Review	x	x	x	x	x	x	x	x	x
Safety Labs			x		x				
Real-time laboratory tests									
Pregnancy testing	x		x				x		
Complete metabolic panel	x		x		x				
CBC/diff	x		x		x				
Coagulation studies Within 6 months of Screen	x								
Hep B surface antigen Within 6 months of Screen	x								
Hep C antibody Within 6 months of Screen	x								
Hep C RNA (if Ab positive) Within 6 months of Screen	x								
Plasma HIV RNA (if HIV+) Within 2 months of Screen	x								
C-reactive protein		x	x		x	x	x	x	x
Erythrocyte sedimentation rate		x	x		x	x	x	x	x
D-dimer		x	x		x	x	x	x	x
Fibrinogen		x	x		x	x	x	x	x
SARS-CoV-2 PCR or Ag test	x	PRN	PRN		PRN	PRN	PRN	PRN	PRN
Stool collection (optional)		x				x		x	x

Target Day	-28	-7	0	1	15	30	90	180	360
Visit Name	Screen	Baseline	Intervention	Phone FU	2W	1M	3M	6M	12M
Visit Window	-28 to -8	-21 to -1	N/A	+1	+/-3	+/-5	+/-14	+/-14	+/-28
Post-hoc laboratory tests									
SARS-CoV-2 antibody testing		x							
Biospecimen storage	x	x	x		x	x	x	x	x
Markers of viral persistence	x	x	x		x	x	x	x	x
Markers of inflammation		x	x		x	x	x	x	x
PK analyses 			x 		x	x	x	x	x

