ADA Immunogenicity 			x		x	x	x	x 	x 
SARS-CoV-2 PCR/Genotyping	x		x		x	x	x	x	x

 Performed pre-dose and post-dose

 Collected pre-dose and 1 hour +/- 10 minutes post dose

 Continue to collect if ADA is detected at previous visit

 PK and ADA post dose sample collection windows:

- D15 (acceptable +/- 3 Days)
- D30 (acceptable +/- 5 Days)
- D90 (acceptable +/- 14 Days)
- D180 (acceptable +/- 14 Days)
- D360 (acceptable +/- 28 Days)

Abbreviations: myalgic encephalomyelitis/chronic fatigue syndrome, ME/CFS; hypermobile Ehler-Danlos Syndrome, hEDS; endometriosis, EM; mast cell activation syndrome, MCAS; DePaul Symptom Questionnaire-Post-Exertional Malaise, DSQ-PEM; postural orthostatic tachycardia syndrome, POTS; pharmacokinetic, PK; anti-drug antibody, ADA.

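### The two rules for late ADA samples conflict, and the governing one (Schedule of Events, footnote 3) either cannot be applied to a post-hoc assay or shows blinded staff an ADA result

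*Combined protocol and SAP*

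**What the plan says.** Section 9.3.4 introduces its sampling list without any condition: "Blood samples for determination of Anti-drug antibodies (ADA)s of AER002 will be collected at following timepoints". The list runs from pre-dose and 1 hour through D15, D30, D90, D180 and D360. Its closing sentence restricts testing only: "If no ADA are detected through Day 90, the D180 and D360 analyses will not be performed". It does not say whether this applies to each participant or to the study as a whole.

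In Appendix 1 the D180 and D360 cells of the ADA row carry footnote 3: "Continue to collect if ADA is detected at previous visit". The row belongs to the block headed "Post-hoc laboratory tests", separate from the real-time tests. Section 9 settles precedence: "The Schedule of Events will serve as the final resource for guiding study activities". Section 10 repeats this for visit content.

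On blinding, section 8.2 states: "Treatment assignments will be blinded to the investigator, subjects, and all clinical and research staff for the entire study". The only exception is designated pharmacy staff or a delegate. It adds: "Subject level unblinded data will not be shared with the Investigator until the end of the trial".

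PK sampling (9.3.3) and biospecimen storage (Appendix 1) are planned at D180 and D360 without condition. The SAP does not mention ADA.

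**The concern.** The two rules differ in what they restrict (testing or collection) and in what triggers them (any result through D90, or the result at the previous visit). Because the Schedule governs, a site following it would omit samples that 9.3.4 still expects the laboratory to test.

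Footnote 3 also needs one visit's result before the next visit. If the assay really is post-hoc, staff cannot apply the footnote. If results are returned in time, being told to draw an ADA tube from a particular participant tells staff that the participant was ADA-positive, and that points towards AER002. The primary safety outcome counts Grade 3 or higher events judged related to treatment over the whole study, and patient-reported outcomes continue to D360. Both depend on the blind after D90.

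**Working it through.** The documents attach no sample size, power or error rate to ADA, so there is no stated figure to reproduce. Three checks apply.

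**1. Do the rules give the same instruction?**

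Inputs: the triggers in 9.3.4 and footnote 3, read per participant, with the previous visit as the immediately preceding one. Each visit is positive or negative. Pre-dose and 1-hour samples are left out.

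- *D180.* Results at D15, D30 and D90 give 2 × 2 × 2 = 8 patterns. 9.3.4 tests D180 if any of the three is positive; footnote 3 collects only if D90 is positive. They differ when D15 and/or D30 is positive and D90 is negative: (+,−,−), (−,+,−) and (+,+,−), so **3 of 8**.
- *D360.* If footnote 3 is followed, the 4 patterns with D90 positive each split by the D180 result (8 patterns), and the 4 with D90 negative have no D180 result (4 patterns), making 12. The rules differ in the 4 with D90 positive and D180 negative, and in the 3 with an early positive and D90 negative: **7 of 12**.
- *Never positive through D90.* Neither rule gives a late ADA result, but 9.3.4 still collects the sample and footnote 3 does not.

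These are counts of patterns, not probabilities.

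**2. What would a known positive tell blinded staff?**

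Allocation is 20 AER002 to 10 placebo (protocol 8.1), so the starting probability of AER002 is 20/30 = 0.667. The documents give neither ADA incidence *i* nor assay false-positive rate *f*; I assume 2-20% and 1-5%.

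P(positive | AER002) = 1 − (1 − i)(1 − f), and P(positive | placebo) = f.

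P(AER002 | positive) = 20·P(positive | AER002) / [20·P(positive | AER002) + 10·f].

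- i = 2%, f = 5%: P(positive | AER002) = 1 − 0.98 × 0.95 = 0.069, giving 1.38 / (1.38 + 0.50) = **0.73**.
- i = 20%, f = 1%: P(positive | AER002) = 1 − 0.80 × 0.99 = 0.208, giving 4.16 / (4.16 + 0.10) = **0.98**.

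With no false positives the answer would be 1.00. The visit windows leave time for results to return: the shortest gap from D90 to D180 is (180 − 14) − (90 + 14) = 62 days.

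**3. ADA first appearing after D90 (per-participant reading)**

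If a share q of the 20 AER002 participants first turn positive after D90, the chance of at least one such case is 1 − (1 − q)^20: 18% at q = 1%, 64% at q = 5% and 88% at q = 10%. These q values are assumptions. The documents give no ADA onset time, half-life or assay drug tolerance, so the calculation shows only that the gap is not negligible by construction.

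**The case against.** Several points on the other side stand.

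- 9.3.4 can be run without touching the blind. The laboratory holds all tubes, assays through D90, then runs or skips the late ones. A reader might infer that both rules expose ADA results to the site; that is true of footnote 3 only.
- Unavailable results and unblinding are alternatives. They cannot both occur for the same sample.
- The post-hoc heading is not proof that nothing in its block is read during the trial. SARS-CoV-2 PCR/genotyping sits there too, marked at screening, and section 6.2 requires a genotype from people who may be chronically infected.
- If the previous visit means any earlier visit, the two triggers coincide. What remains is that one rule restricts collection and the other testing, together with the blinding problem. If 9.3.4 is study-wide, a single positive through D90 lifts its restriction, while footnote 3 applied per participant would still leave most samples undrawn.
- ADA is not a listed endpoint, the trial is exploratory with 30 participants, and conditional late testing is a permissible choice.

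Stronger inferences are tempting but unsupported. That ADA incidence would be biased low because circulating drug masks antibody depends on assay and half-life facts not in the documents. That 270 of 360 days (75%) go unassessed treats two sparse visits as continuous coverage. That late ADA is lost for good overlooks the PK and stored blood taken at both visits, although nothing commits that blood to ADA testing.

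**Conclusion.** The concern holds in a limited form. The ADA texts conflict and need reconciling. On the readings stated, they diverge for D180 in 3 of 8 patterns, and the Schedule's precedence means samples 9.3.4 would test might not exist. Footnote 3 as written is either unworkable or a route to partial unblinding. A positive result is strong but not conclusive evidence of AER002 (about 0.73-0.98 against 0.67 beforehand, under the assumed rates).

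The exposure is confined to relatedness judgements and patient-reported outcomes after D90, in however many participants are ADA-positive, a number the documents do not give. A reader might infer that the D90 PROMIS-29 result is at risk. It is not, because conditional collection starts at D180.

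On the per-participant reading, ADA first appearing after D90 is not planned to be tested. How often that would matter cannot be judged from the documents.

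**What to change.** Delete footnote 3, and collect and store ADA serum at D180 and D360 for every participant. Run ADA testing in batches in the laboratory, with results withheld from blinded staff until the trial is unblinded.

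Preferably, also drop the closing sentence of 9.3.4 and test D180 and D360 for all. This adds at most 30 × 2 = 60 assays (20 × 2 = 40 in the AER002 arm), at visits where PK and storage blood is already taken. That is the small downside, besides a minor amendment.

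If conditional testing is kept, apply it only in the laboratory, state whether it is per participant or study-wide, and report that ADA onset after D90 was not assessed in those not tested.

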### **9.3.5 SARS-CoV-2 Genotyping**

Genotyping may be performed on any samples collected during the study in which SARS-CoV-2 virus is recovered.

## **9.4 Biospecimens**

Within the UCSF LIINC infrastructure, initial sample processing is performed on peripheral blood units which are then transported by a staff member or courier to a biorepository, which include the Molecular and Cellular Core (formerly Core Immunology Laboratory) and the UCSF Specimen Processing and Banking Subcore (formerly AIDS Specimen Bank). All samples are tracked through laboratory information systems and managed with sample storage inventories, monthly reports, and institutionally managed data storage and back-up systems. All biospecimens will eventually be stored long-term via the UCSF Specimen Processing and Banking Subcore (formerly AIDS Specimen Bank), where the existing 50,000-specimen LIINC repository is currently housed and managed. Specimens are stored in ultra-low temperature freezers (including liquid nitrogen) with back-up power systems, in which temperature is monitored by a programmable scanning alarm system wired to the university's telephone system. After completion of the primary analyses, samples may be stored indefinitely via the LIINC biorepository for use on other COVID-related pathogenesis studies (as addressed in the consent form), at the discretion of the PI.

## **10 EVALUATIONS BY VISIT**

The details of the visit schedule are outlined below. The Schedule of Events will be the final guide for what events are to occur at each specific study visit.

### **10.1 Screening Visit (D-28)**

Following the informed consent discussion and signed informed consent form, the Screening Assessment will be performed. The inclusion and exclusion criteria will be reviewed with the participant. Screening labs, medical history (including assessment for conditions that intersect with Long COVID), and the details of concomitant medications will be obtained. Details of the participant's COVID-19 history will be reviewed and/or confirmed.

The Screening Assessment will include a physical assessment by a study clinician (physician, nurse, or physician assistant). A symptom assessment, PROMIS-29, and Duke Activity Status Index will be performed as part of the Screening procedures.

Laboratory tests as outlined in the Schedule of Events will be performed. Laboratory tests or other assessments performed for a clinical indication (not exclusively to determine study eligibility) may be used for screening values even if the studies were performed before informed consent was obtained. An individual who recently had laboratory tests performed as part of routine clinical care need not repeat these tests if they are within the window. For example, someone with recent Hepatitis B or C or HIV testing may not need to have the test repeated, as indicated in the Schedule of Events. However, these measurements may be repeated at the discretion of the PI.

Screening evaluations should be completed within 28 days of D0. If more than 28 days lapse, screening procedures may be repeated to re-confirm eligibility prior to D0. At a minimum, this will include the metabolic panel, complete blood count, and pregnancy testing. Laboratory tests that are not expected to change (such as coagulation studies or viral hepatitis status) are not required to be repeated but may be at the discretion of the PI.

If needed to reduce participant burden (at the request of the participant or investigator team) the assessments from the Screening Visit may be conducted over two visits during the screening period, but all Screening assessments must be completed to confirm eligibility prior to the conduct of the procedures from the Baseline visit.

Rescreening: A participant who does not meet all eligibility criteria at the time of Screening may be given the opportunity to rescreen for the study at a later date.

## **10.2 Baseline Evaluation (D-7)**

An additional visit will be performed following Screening, at least 7 days after the screening visit and prior to D0. The target date for this visit is within 7 days prior to the scheduled date of study product administration, although up to 21 days is acceptable. The purpose of this visit is to make additional assessments prior to the intervention, to establish baseline symptomatology and measurements. This will include a symptom assessment and various clinical assessments as outlined in the Schedule of Events. Certain real-time laboratory tests will be obtained to establish a baseline.

If needed to reduce participant burden (at the request of the participant or investigator team) the assessments from the Baseline Visit may be conducted over two visits during the baseline period, but all Baseline assessments must be completed prior to the day of the infusion visit.

## **10.3 Intervention (D0)**

Participants who screen into the study and complete baseline measurements will be randomized to receive either AER002 or placebo. They will complete a symptom assessment. During the D0 visit prior to infusion or at the reminder call prior to that visit, a team member will confirm that there have been no major changes to the participant's health since the baseline visit that would affect eligibility. If there have been major changes, this will be discussed with a study clinician prior to infusion to confirm whether or not it is acceptable to proceed.

Vital signs will be performed as follows:

- (1) Within approximately 1 hour prior to administration of the study product.
- (2) Within approximately 20 minutes of completion of the administration of the study product.
- (3) Prior to departure from the unit at which the infusion is administered.
- (4) As needed at any other point during the visit, at the discretion of the staff or the PI or in the case of concerning signs or symptoms experienced by the participant.

The PI and/or study nurse should be notified for further guidance if any of the following vital sign abnormalities are confirmed on repeat measurement:

- (1) Temperature >38 degrees Celsius.
- (2) Resting heart rate >120 or <40 beats per minute.
- (3) Resting systolic blood pressure >180 or <85 mmHg.
- (4) Resting respiratory rate >30 breaths per minute.
- (5) Resting oxygen saturation <90%.

In such a case, the PI will provide guidance on how to proceed. In general, the above abnormalities must resolve prior to administration of the study product and prior to participant discharge from the unit.

Participants will be observed for at least 120 minutes following the product administration and provided with return precautions should they develop any concerning signs or symptoms over the subsequent 24 hours.

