## 5.2 Safety Evaluations

- Number of participants with adverse events (AE)s (Treatment Emergent Adverse Events (TEAE)s, Serious Adverse Events (SAE)s, and Adverse Events of Special Interest (AESI)). The primary outcome will be the number of individuals in each group experiencing a severe (Grade 3 or greater) AE thought to be possibly, probably, or definitely related to study treatment throughout the study duration. Specific AESI and their associated symptoms experienced with IV infusions include the following:
  - Immune-mediated AEs include Type I – Type IV hypersensitivity reactions. Types I-III occur within the first 24 hours of exposure and are considered immediate reactions. Type IV are considered delayed. They can occur up to 72 hours post exposure.
  - Type I hypersensitivity reactions manifest as anaphylaxis, urticaria, and angioedema.
  - Type II hypersensitivity reactions involve cell depletion and/or destruction without inflammation.
  - Type III hypersensitivity reactions involve immune complexes causing serum sickness type reactions.
  - Type IV hypersensitivity reactions are cell mediated inflammatory responses.
  - Cytokine release syndrome – may mimic anaphylaxis and present with hypotension, urticaria, and an overall hyperinflammatory response.

NOTE: None of the AESI have occurred with the study drug as part of the ongoing Phase 1 Clinical Trial COV-2022-001.

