#### **8.4.3 Administration Instructions**

The date and time of each dose will be recorded. For each participant, all scheduled post-dose activities and assessments will be performed at the end of study drug infusion.

The assigned IP will be admixed in 250 mL of NaCl 0.9%. and infused IV over 30 minutes.

Additional administration instructions are included in the pharmacy manual.

The site where administration occurs must have resuscitation equipment, emergency drugs and appropriately trained staff available during the IV infusion of study product.

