### 9.1.6 Questionnaire-based Measurements

**Medical History Questionnaires.** As part of the medical history at the Screening Visit, participants may be assessed for several medical conditions thought to be related to Long COVID. These may include questions or checklists about chronic fatigue symptoms, hypermobility symptoms, endometriosis symptoms (ENDOPAIN-4D scale) and mast cell activation syndrome (Mast Cell Activation Questionnaire).

**Long COVID Symptom Assessment.** Signs and symptoms related to Long COVID will be reviewed at all visits, using the LIINC CRFs. This will include the presence and absence of Long COVID symptoms within the prior 30 days and the prior 2 days, as well as information about how bothersome the symptoms are. Long COVID symptoms are one of the primary outcomes of the study.

**Other Symptom Assessment (AE Review).** In addition to Long COVID symptoms, at D0 and all subsequent visits, all grades of signs and symptoms that are newly developed or changed since the previous visit will be recorded. Symptoms not previously experienced as part of Long COVID, or which have worsened beyond the degree previously experienced by the participant, will be considered to represent adverse events and recorded as such. For these symptoms, duration (start and stop dates), severity/grade, outcome, treatment, and relation to study drug will be recorded on the case report forms. All clinical events and new diagnoses or changes in diagnoses should be recorded.

**Quality of Life.** Quality of life (QoL) will be obtained using a scale such as the EQ-5D-5L scale which is part of the LIINC CRFs. This will include the 100-point visual analogue scale (VAS).

**PROMIS-29.** The PROMIS-29 form will be completed as outlined in the schedule of events. This scale measures self-reported health, using a collection of short forms assessing fatigue, physical function, anxiety, depression, pain, sleep disturbance, and ability to participate in social roles and activities. The questionnaire uses a computer interface over approximately 5 minutes. It is available in English and Spanish. This instrument has been used for ME/CFS and Long COVID.

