#### **10.4 Telephone Follow-up (Phone Follow-Up, D1)**

The participant will be contacted by telephone to check on the overall response to the infusion. This will include the DSQ-PEM instrument administered over the phone to assess post-exertional symptoms.

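### Return precautions after the infusion are stated for 24 hours, but the plan's own window for delayed (Type IV) hypersensitivity runs to 72 hours

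*Combined protocol and SAP*

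**What the plan says.** Three parts of the plan bear on this.

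- **Infusion visit.** Section 8.4.3 has the product "infused IV over 30 minutes". Under section 10.3, "Participants will be observed for at least 120 minutes following the product administration", after which they are "provided with return precautions should they develop any concerning signs or symptoms over the subsequent 24 hours".
- **AESI definitions.** Section 5.2 lists Type I to Type IV hypersensitivity as AESIs and gives two onset windows. For the immediate reactions: "Types I-III occur within the first 24 hours of exposure and are considered immediate reactions". For the delayed ones: "Type IV are considered delayed. They can occur up to 72 hours post exposure". SAP section 2.3 repeats both.
- **Contacts after discharge.** Section 10.4 describes the D1 call: "The participant will be contacted by telephone to check on the overall response to the infusion". The DSQ-PEM is also given at that call. The Schedule of Events (Appendix 1) allows the call a window of +1 day and marks an adverse event review for it. The next scheduled contact is the D15 visit, with a window of +/-3 days. The footnote on PK and ADA samples gives the same window: "D15 (acceptable +/- 3 Days".

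No section of the available text states a longer period for the return precautions.

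**The concern.** The period in section 10.3 covers the immediate reactions and stops close to where the window specific to delayed reactions begins. The plan recognises Type IV hypersensitivity as a reaction to look for and says how late it can appear, yet the stated instruction to participants does not reach that far.

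At stake is how soon a participant seeks care and how soon the team hears. Section 2.3.1 warns that allergic reactions can occur after the infusion and may be severe; the safeguard it names is the 120-minute observation. After discharge, section 10.3 relies on participants to recognise symptoms and act on them. Someone whose reaction starts after the D1 call has no scheduled contact until D15.

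The safety clocks also depend on awareness. The Safety Monitoring Committee (SMC) review in section 14 is due within 3 business days of learning of a triggering event, and the manufacturer is notified within 24 hours of the investigator becoming aware of an SAE (section 11.2.1). Late reporting would start both late.

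**Working it through.** No power or sample size figure is involved. The check sets the plan's time windows against each other.

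**Inputs**

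| Item | Value | Source |
|---|---|---|
| Infusion | 0.5 h | Protocol 8.4.3 |
| Minimum observation | 120 min = 2 h | Protocol 10.3 |
| Return precautions | 24 h | Protocol 10.3 |
| Type I-III onset | 0-24 h | Protocol 5.2, SAP 2.3 |
| Type IV onset | up to 72 h | Protocol 5.2, SAP 2.3 |
| D1 call | D1 to D2 (+1 day) | Appendix 1 |
| D15 visit | D12 to D18 (+/-3 days) | Appendix 1 |

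**Step 1: when the stated precautions end.** The text does not fix the starting point, so both readings are shown.

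- Counted from the infusion: 24 h.
- Counted from the end of minimum observation: 2 + 24 = 26 h.
- The second reading measured from the start of the infusion: 0.5 + 2 + 24 = 26.5 h.

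**Step 2: how much of the 72 hours lies beyond that.**

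- 72 - 24 = 48 h, and 48/72 = 66.7%.
- 72 - 26 = 46 h, and 46/72 = 63.9%.
- With the infusion time included, 72 - 26.5 = 45.5 h, and 45.5/72 = 63.2%.

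**Step 3: split by reaction type.** The Type I-III window (0-24 h) is covered in full. The part that only delayed reactions occupy is 72 - 24 = 48 h. Of this, 0 to 2 h are covered (2.5 h if measured from the start of the infusion).

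**Step 4: what the D1 call adds.** Assume that D1 and D2 correspond to 24 and 48 hours post-infusion.

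- Type IV window still ahead after the call: 72 - 48 = 24 h to 72 - 24 = 48 h.
- Gap from the call to the next scheduled contact: 12 - 2 = 10 days to 18 - 1 = 17 days.

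The call can pick up a reaction already under way. It cannot pick up one that starts later, and section 10.4 does not say that the precautions are repeated.

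**Step 5: whether events would be lost from the data.** They would not be lost for this reason. Section 9.1.6 provides that, at D0 and every later visit, "all grades of signs and symptoms that are newly developed or changed since the previous visit will be recorded". Section 9.1.7 captures adverse events throughout the study, and section 10.6 allows unscheduled visits. A delayed reaction would still be recorded at D15 at the latest if that visit takes place.

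**The case against.** The best case for the current text is that 24 hours was a considered choice. The precautions follow directly from the 120-minute observation, which section 2.3.1 ties to acute allergic reactions and cytokine release syndrome, and the plan's immediate reactions fall within 24 hours. As that period ends, staff telephone the participant and review adverse events, so there is a handover. Nothing tells participants to ignore later symptoms, and unscheduled visits are available. The consent form, where contact advice normally sits, was removed from the available documents and may already give a longer period. Section 5.2 notes that none of the AESIs had occurred in the ongoing Phase 1 trial, and no Type IV rate is given, so a share of clock hours says nothing about the number of people affected.

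Much of this stands, and it limits the weight of the point. What participants are told elsewhere cannot be judged, so the effect on care-seeking is possible and not shown. The Phase 1 note suggests that such events will be infrequent. Observation is a minimum, so longer stays would shift the end point somewhat.

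None of it removes the mismatch. The call may come with 24 to 48 hours of the Type IV window still to run. The Phase 1 note bears on frequency, and the plan still lists Type IV reactions with a 72-hour window. If the consent form already says 72 hours, the protocol should agree with it.

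**Conclusion.** The concern holds as a mismatch within the protocol text. The precautions named in section 10.3 leave 46 to 48 of the 72 hours uncovered (64-67%), and they cover at most 2 of the 48 hours specific to delayed reactions. Including the infusion time moves these figures by half an hour and changes nothing of substance.

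The conclusion rests on reading the 24 hours as the end of the stated instruction and on the available text alone. It is a minor participant-safety point that should be corrected because the plan's own AESI window calls for it. The possible consequence is later care-seeking and later reporting of a delayed reaction. The primary endpoint, its analysis and the statistical design do not depend on it.

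**What to change.** Two edits:

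1. In section 10.3, replace the 24-hour period for return precautions with at least 72 hours after the infusion. This matches the Type IV window in section 5.2 and SAP section 2.3 and settles the starting point.
2. In section 10.4, add a sentence that staff repeat these return precautions at the D1 call.

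The cost is one phrase and one sentence. Visits, calls, staffing, endpoints, analysis and sample size stay as they are.
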